4.7.2 Reporting of Adverse Events

The procedure for reporting any AE is as follows:

- All Adverse events will be documented on an Adverse Event Form
- The Investigator is responsible for reporting AEs to his or her IRB in accordance to their site's IRB procedures.
- The Investigator shall report all unanticipated adverse device effect to the Monitor/Sponsor as soon as possible, but definitely no later than 10 days after obtaining knowledge of event.
- The Sponsor is responsible for informing the FDA, all reviewing IRBs and other investigators of any unanticipated adverse device effect that has occurred.

4.8 Device Failures and Malfunctions

4.8.1 Definition: A Device failure is defined as the inability of the device to perform its intended function. Device failures can result from hardware/software problems or surgical procedure problems.

4.8.2 Reporting and Return: All failures and malfunctions will be documented on the CRF and reported in the clinical results. *Esteem® System* devices that fail or malfunction will be returned to the Sponsor for analysis.

If at all possible, a representative from the Sponsor will be present for the removal of an *Esteem® System* due to a failure or malfunction.

5 STATISTICAL ANALYSIS

5.1 Sample Size

For the effectiveness objectives, based upon the following analysis and 0204 clinical data, a sample size of 45 new subjects meets the guidelines for statistical power. For the facial pareses/paralysis objective with an end point of 1 month, a sample size of 109 subjects is required as shown below.

SRT

Based on a mean improvement in SRT over hearing aid of 10 dB and a standard deviation of 13 dB, 45 subjects at 1 year would provide at least 80% power for testing non-inferiority and superiority at a one-sided 0.05 alpha level. A margin of – 5 dB will be used for non-inferiority and a margin of +5 dB will be used for superiority.

WRS

Based on a mean improvement in WRS over hearing aid of 22% and a standard deviation of 31, 45 subjects at 1 year would provide at least 80% power for testing non-inferiority and superiority at a one-sided 0.05 alpha level. A margin of –10% will be used for non-inferiority and a margin of +10% will be used for superiority.

Facial Pareses/paralysis:

Based upon a null hypothesis of 7% and a hypothesized true rate of 2% of facial paresis/paralysis, 109 subjects at 1 month would provide at least 80% power for testing the hypothesis.

5.2 Objective Analysis

The following statistical analyses will be done.

Objective 1: To determine whether the *Esteem® System* improves the subjects' threshold of sensitivity for hearing and identifying speech signals as well as or better than the pre-implant conventional hearing aid.

Endpoint: Comparison of the subjects' speech reception threshold using the subjects' pre-implant aided condition as compared to the *Esteem®* at follow-ups of 4 months to 1 year.

Criterion for Non-Inferiority- The 95% Lower Confidence Bound (LBC) for the mean difference between the SRT at baseline versus follow-up ($\mu_{\text{Pre-implant aided}} - \text{follow-up}$) is greater than or equal to -5 dB.

$$95\% \text{ LCB for } \mu_{\text{Pre-implant aided}} - \text{follow-up} \geq -5$$

Criterion for Superiority- The 95% Lower Confidence Bound (LCB) for the mean difference between the SRT at baseline versus follow-up ($\mu_{\text{Pre-implant aided}} - \text{follow-up}$) is greater than +5 dB.

$$95\% \text{ LCB for } \mu_{\text{Pre-implant aided}} - \text{follow-up} > +5$$

Category Analysis: In addition, the results will be categorized by level of improvement, showing % of subjects at each improvement/unimprovement category compared to pre-implant aided condition with the categories of improved/unimproved based on the +/- 5 dB margins.

Objective 2: To demonstrate that the *Esteem® System* is as effective as or better than the hearing aid for improving speech discrimination (intelligibility) as shown by the word recognition score at 50 dB.

Endpoint: Comparison of the word recognition score using the *Esteem®* compared to the pre-implant aided condition at follow-up from 4 months to 1 year.

Criterion for Non-Inferiority- The 95% Lower Confidence Bound (LBC) for the mean difference between the WRS at baseline versus follow-up ($\mu_{\text{Pre-implant aided}} - \text{follow-up}$) is greater than or equal to -10%.

$$95\% \text{ LCB for } \mu_{\text{Pre-implant aided}} - \text{follow-up} \geq -10\%$$

Criterion for Superiority- The 95% Lower Confidence Bound (LCB) for the mean difference between the WRS at baseline versus follow-up ($\mu_{\text{Pre-implant aided}} - \text{follow-up}$) is greater than +10%.

$$95\% \text{ LCB for } \mu_{\text{Pre-implant aided}} - \text{follow-up} > +10\%$$

Additional Analyses: The Word Recognition Scores will be compared using the Thornton and Raffin (1978) published upper and lower limits for various word lists based upon percentage scores. Based upon this, an analysis of the % better than, % equal to and % below the aided condition (HA) will be presented.

Reference:

Objective 3: To determine the incidence rate of Serious Adverse Device Effects (SADE) and the incidence rate of device failures and replacements.

Endpoint: The analysis of the incidence of SADEs and device failures and replacements at each follow-up.

Hypotheses: There is no formal hypothesis. This objective is to provide an accurate estimate of the SADE rate and device failure and replacement rate associated with the *Esteem® System*.

Statistical Analyses: The incidence of SADEs and device failures and replacements will be estimated with the observed number of SADEs and device failures and replacements over the total person-months of follow-up at each follow-up. The upper bound of the one-sided 95% exact binomial confidence interval on the SADE rate and device failure and replacement rate will be calculated and reported.

Objective 4: To demonstrate that the incidence of facial pareses/paralysis is no greater than the 7% incidence experienced in the PMA clinical trial.

Endpoint: The analysis of the incidence of facial pareses/paralysis at 1 month follow-up.

Criterion for success: The 95% Upper Confidence Bound (UCB) for the incidence of facial paresis/paralysis ($p_{\text{paresis/paralysis}}$) is less than 7%

$$95\% \text{ UCB for } p_{\text{paresis/paralysis}} < 7\%$$

Statistical Analyses: The upper bound of the one-sided 95% exact binomial confidence interval on the incidence of facial paresis/paralysis will be compared to 7% and success declared if it is lower than 7%.

Objective 5: To demonstrate that the subject's cochlear function remains unchanged with the *Esteem®* system as shown by comparison of the subject's pre-implant baseline Bone Conduction Threshold (BCT) vs. the subject's post activation BCT.

Endpoint Analysis: Bone conduction will be measured with forehead probe placement. The Safety Algorithm as described in Attachment C, will be used for any Bone Conduction results outside the stability range.

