1.5 Duration of the Investigation

The post-approval study will commence immediately upon PAS Protocol approval. Subjects will be followed at 1, 4 and 10-months post-activation and annually thereafter through 1 year.

2 STUDY DESIGN AND OVERVIEW**2.1 Trial Design**

This Post Approval Study is designed as a prospective, multi-center, non-randomized, clinical trial to evaluate the safety and efficacy of the *Esteem® System* implanted by newly-trained surgeons. For this trial the subject will act as his or her own control.

This trial has been designed to meet United States' regulatory requirements.

Each subject will act as both the test subject and the control by being tested prior to implant in both the unaided and aided condition.

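### The word recognition (WRS) success criteria in section 5.2 subtract in the wrong direction, so applied literally they fail a device that helps and can call a harmful one superior

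*Combined protocol and SAP*

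**What the plan says.** Section 5.2 gives Objective 2 two criteria, each a threshold for the one-sided 95% lower confidence bound. The superiority criterion concerns the "Lower Confidence Bound (LCB) for the mean difference between the WRS at baseline versus follow-up" and requires the bound to exceed +10%. The non-inferiority criterion carries the contrast in its formula: "\mu_{\text{Pre-implant aided}} - \text{follow-up}$) is greater than or equal to -10" percent. The order is pre-implant first and follow-up second in all four places, namely both sentences and both display formulas. Objective 1 (SRT) uses the same contrast, with margins of -5 and +5 dB.

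Section 5.1 sets the WRS sample size on a different footing: "Based on a mean improvement in WRS over hearing aid of 22% and a standard deviation of 31". It then fixes the margins: "A margin of –10% will be used for non-inferiority and a margin of +10% will be used for superiority". It concludes that "45 subjects at 1 year would provide at least 80% power for testing non-inferiority and superiority at a one-sided 0.05 alpha level". There, a positive number means the device did better than the hearing aid. Nothing elsewhere in the document defines the WRS difference again or reverses its sign.

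**The concern.** SRT is a threshold in dB. A fall is a benefit, so pre-implant minus follow-up is positive when the device helps, and a lower bound compared with -5 or +5 dB does what is intended. WRS is a percent-correct score and runs the other way: inclusion criterion (e) in section 4.1.1 sets a minimum score, and Objective 2 seeks a result as good as or better than the hearing aid's. For WRS, the same subtraction measures loss rather than gain.

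Placing a lower bound on loss turns the test around. The non-inferiority criterion no longer rules out a loss of more than 10 points. It asks instead that the data rule out a gain of more than 10 points. The superiority criterion is met when the data show, with 95% confidence, a loss of more than 10 points. This is a primary effectiveness objective, and the written criterion is what fixes the claim in advance.

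**Working it through.** **Inputs.** From section 5.1: mean improvement 22 points, SD 31, n = 45, one-sided alpha 0.05, margins -10 and +10. From section 2.1: each subject is his or her own control, so the analysis is a one-sample analysis of paired differences. The SD of 31 is taken as the SD of those differences, a reading the reproduced power supports.

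**Common quantities.**
- SE = 31/√45 = 4.62.
- The t critical value on 44 df is 1.680, so the bound lies 1.680 × 4.62 = 7.76 points below the observed mean.
- P(bound exceeds margin) ≈ Φ((μ − margin)/SE − 1.645), checked with the noncentral t.

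**The plan's own figure, with improvement positive (μ = +22).**
- Superiority: (22 − 10)/4.62 = 2.597; 2.597 − 1.645 = 0.952; power 0.829 (normal) or 0.819 (t).
- Non-inferiority: (22 + 10)/4.62 = 6.925; power above 0.9999.

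The stated power of at least 80% is therefore reproduced, but only for follow-up minus pre-implant.

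**The section 5.2 rule as written (pre-implant minus follow-up).**

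| True effect on WRS | μ in the written contrast | Expected bound | P(non-inferiority met) | P(superiority met) |
|---|---|---|---|---|
| Gain of 22 | -22 | -22 − 7.76 = -29.8 | 0.000013 (t); 0.000011 (normal) | effectively 0 |
| No change | 0 | -7.8 | 0.69 (t) | 0.00008 (t) |
| Loss of 22 | +22 | 22 − 7.76 = +14.2 | above 0.9999 | 0.819 (t); 0.829 (normal) |

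For the first row, non-inferiority is (-22 + 10)/4.62 − 1.645 = -4.24, and Φ(-4.24) is about 0.00001. The no-change row is the same under either direction.

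**The edge of the intended margin.** At a true loss of exactly 10 points, non-inferiority should be declared 5% of the time. As written, (10 + 10)/4.62 − 1.645 = 2.68, so it is declared with probability 0.996 (normal).

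**In terms of the observed mean, if the sample SD is 31.**
- Non-inferiority fails for any observed gain above 10 − 7.76 = 2.2 points.
- Superiority is met for any observed loss above 10 + 7.76 = 17.8 points.

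**SRT for comparison.** With a mean of 10 dB, SD 13 and margin +5, SE = 13/√45 = 1.94 and superiority power is 0.825 (normal) or 0.815 (t). The SRT direction agrees with section 5.1.

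**The case against.** The best defence is that this is a slip of notation with an obvious intent. Section 5.1 puts WRS on an improvement scale, the stated power reproduces only on that scale, and Objective 2 is worded in terms of benefit. An analyst would probably compute follow-up minus pre-implant without comment. A reversed result would also be conspicuous, because section 5.2 separately asks for the percentages of subjects better than, equal to and below the hearing aid, judged against published limits for word-list scores. The phrase about baseline versus follow-up carries no sign in itself, and the typesetting of the subscripts is imperfect.

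Much of this stands. The intent is recoverable, the sample size is sound, and the extreme probabilities describe literal application rather than a likely report. But the notation argument is weak: the same expression works as an ordinary subtraction for SRT, and broken subscripts do not explain an identical order in four places. The responder table would expose the contradiction without saying which result governs. Relying on the analyst to reverse the sign means departing from a prespecified primary criterion, possibly with the data in hand.

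**Conclusion.** The concern holds. Both WRS criteria are wrong in sign as written and contradict section 5.1. Taken literally, a device performing exactly as planned meets non-inferiority about once in 100,000 trials and superiority essentially never, whereas one that lowers WRS by 22 points is declared superior with probability 0.82. These figures rest on section 5.1's SD of 31, 45 evaluable subjects and a paired t-based bound. The reversal itself rests on none of them, because it follows from the direction of the subtraction. The correction should be made before the WRS data are analysed.

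**What to change.** In Objective 2 of section 5.2, in both sentences and both display formulas, define the difference as follow-up (Esteem) minus pre-implant aided. Non-inferiority is then met if the one-sided 95% lower bound is at least -10%, and superiority if it is above +10%. Add a line saying that a positive WRS difference means improvement. Leave the SRT criteria unchanged.

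With this change the power is above 0.999 for non-inferiority and 0.82 for superiority (t), consistent with section 5.1. The cost is an edit to two criteria. Sample size, margins, alpha, visits and data collection stay as they are.

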4.3.3.3 Intra-operative System Testing

The complete *Esteem® System* will be tested.

- a) Interrogate the Sound Processor prior to opening the non-sterile shelf carton. If the Sound Processor does not respond to interrogation, do not use and return to Envoy Medical.

The following testing will be performed after the leads have been connected to the Sound Processor and prior to wound closure. The surgical site must be keep free of all fluids and as dry as possible during the system test to reliably collect valid test data.

- b) Connect the Sensor and Driver connectors to the Sound Processor. Verify that the lead terminal pins are completely inserted into the SP lead barrels (the pin will be visible past the connector block).
- c) Program the Sound Processor to perform the system test.
- d) Perform the system test at 80 dB according to the ISA.
- e) Record the system test results.
- f) After completion of all testing, program the Sound Processor volume step to "OFF"

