4.5.2 Activation Visit (8 weeks ± 2 week post implant)

At the Activation visit, the subject will be evaluated to ensure proper healing of the middle ear and around the implanted Sound Processor. The device will be turned on to begin the acclimation period. An audiogram will be performed along with an *Envoygram* to ensure that the device is providing the subject with some benefit.

The testing required at the Activation Visit is outlined in Table 1.

A personal programmer will be provided to the subject and he or she will be instructed on how to use the Personal Programmer prior to leaving the clinic.

Due to the nature of Middle Ear surgery and potential requirements for multiple revisions, the surgical procedure may require a second procedure or "revision" to properly adhere the driver to the stapes. The procedure will be considered complete once the driver to the stapes connection has been determined to be successful by the surgeon. All revision surgeries will be reported as clinical procedure failures.

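### Objective 3 reports SADEs and device failures or replacements only per person-month, with no stated time origin; a cumulative percentage of implanted subjects would answer the safety question and fit the planned binomial bound

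*Combined protocol and SAP*

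**What the plan says.** Objective 3 in section 5.2 concerns serious adverse device effects (SADEs) and device failures and replacements. On testing it says "There is no formal hypothesis". On purpose it says "This objective is to provide an accurate estimate of the SADE rate and device failure and replacement rate". The incidence "will be estimated with the observed number of SADEs and device failures and replacements over the total person-months of follow-up at each follow-up". For uncertainty, the plan computes and reports "The upper bound of the one-sided 95% exact binomial confidence interval on the SADE rate and device failure and replacement rate".

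Other sections bear on the time axis. At the end of surgery (section 4.3.3.3) the instruction is "After completion of all testing, program the Sound Processor volume step to" OFF. Section 4.5.2 is headed "Activation Visit (8 weeks ± 2 week post implant") and says of that visit "The device will be turned on to begin the acclimation period". Section 4.5.3 times the later visits at 1, 4 and 10 months from activation. Section 4.5 describes follow-up as beginning after implant, yet Table 1 in section 4.6 marks adverse events only from the Activation visit onward.

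Section 4.8.1 counts failures that come from the surgery as well as from hardware or software. Section 4.5.2 foresees revision of the driver attachment. Sections 2.2 and 4.7 bring the safety population to 109 by adding retrospective charts of commercial patients to the 45 new subjects.

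**The concern.** The Protocol Summary asks whether the device is safe through 1 year. A surgeon, patient or regulator will want to know what share of implanted people had a SADE, a failure or a further operation by a given time. Section 3.2 already speaks in those terms: 5% revision, 2% explant, and a revision risk of up to 7%. A rate per person-month cannot be set beside these figures without conversion.

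Three features of the estimator cause the difficulty.

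- **Constant risk.** One rate over all follow-up averages an early period dominated by surgery and healing with a later, presumably quieter one. It understates early risk and overstates late risk. If it is cumulative, its decline across visits can be read as improving safety.
- **Undefined clock.** Implant and activation are 8 ± 2 weeks apart. From activation, SADEs of surgery and healing have no matching time at risk. From implant, failures that can appear only in an active device are divided by time in which they could not appear.
- **Mismatched bound.** An exact binomial interval needs a number of subjects, each with the event or without it. Person-months are not such trials, and one subject may have several events.

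**Working it through.** **Plan's own figure.** Objective 3 states no expected rate, sample size or limit. The only safety sample size, 109 in section 5.1, was derived for Objective 4 (7% against 2%). It reproduces with the exact one-sided 95% bound: at most 3 events in 109 (upper bound 6.96%) and power 82.5%. It says nothing about Objective 3.

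**Inputs.** Activation at 8 weeks, range 6 to 10 (section 4.5.2); visits at 1, 4 and 10 months after activation (section 4.5.3); 45 new subjects (section 2.2). Assumptions: 5 subjects with one event each, all by the 1-month visit; complete follow-up. The documents give no expected count.

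**Time.** 8 × 7 / 30.4375 = 1.84 months (1.38 to 2.30 for 6 to 10 weeks).

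**Step 1: cumulative rate by visit.** Rate = 5 / (45 × months since origin).

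| Visit after activation | Person-months from implant | Per 100 person-months, implant clock | Per 100 person-months, activation clock | Subjects affected |
|---|---|---|---|---|
| 1 month | 45 × 2.84 = 127.8 | 3.91 | 5/45 = 11.1 | 5/45 = 11.1% |
| 4 months | 45 × 5.84 = 262.8 | 1.90 | 5/180 = 2.78 | 11.1% |
| 10 months | 45 × 11.84 = 532.8 | 0.94 | 5/450 = 1.11 | 11.1% |

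On the implant clock the fall is 11.84 / 2.84 = 4.2-fold. With activation at 10 or 6 weeks it is 12.30 / 3.30 = 3.7 or 11.38 / 2.38 = 4.8. While all events precede the 1-month visit, this ratio does not depend on the number of subjects or events. On the activation clock the fall is tenfold. No events are lost: 0.94 per 100 × 11.84 months returns 11.1 per 100 subjects, but the reader has to do that conversion.

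**Step 2: per-interval reading.** If each figure covers only the time since the previous visit, the implant-clock rates are 3.91, 0 and 0. The early peak stays visible, and 3.91 × 2.84 = 11.1 per 100 recovers the share affected. The plan does not say which reading applies.

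**Step 3: dilution of failures that need an active device.** If all 5 events were such failures and all arose after activation, the implant clock gives 5/532.8 = 0.94 and post-activation time gives 5/450 = 1.11 per 100 person-months. The ratio is 10 / 11.84 = 0.845, about 16% lower (12% to 19% for 6 to 10 weeks). This holds only if none arises before activation. If pre-activation events are removed together with their time, the rate rises only when fewer than 1.84 / 11.84 = 15.5% of events fall there. With 2 of 5 before activation it drops from 0.94 to 3/450 = 0.67.

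**Step 4: the bound.** One-sided 95% upper bounds for 5 events at 10 months on the implant clock:

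- exact binomial on 45 subjects: 22.0% of subjects
- exact binomial treating 533 person-months as trials: 1.96 per 100 person-months
- exact Poisson on the same time: 1.97 per 100 person-months

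The last two nearly agree because events are rare. The first is a different quantity, and the plan does not say which denominator its binomial bound uses.

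**The case against.** The strongest reply is that little turns on this. Objective 3 has no hypothesis or success limit. Facial paresis or paralysis, a prominent early surgical harm, is already assessed per subject at 1 month under Objective 4 with a pass limit. The rate is to be reported at each follow-up, so the early visits would show the high early figure, and on a per-interval reading nothing is spread over the year. All of this stands and limits the point to reporting and interpretation. It does not supply the missing per-subject percentage, and it leaves the reading of the rate open.

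A reader might infer that switched-off time makes both rates look better than they are. The documents do not support that.

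- Section 5.2 never says that the roughly 8 weeks before activation are counted.
- For SADEs of surgery and healing those weeks are real time at risk. If an activation clock left them out while the events were kept, the SADE rate would be too high.
- For device failures they are partly time at risk as well, because section 4.8.1 includes failures caused by the surgery.

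A reader might also compute that the failure rate is understated nearly threefold at the 1-month visit (2.84 / 1 = 2.84). That needs an implant clock and no failure of any kind before activation, and the documents establish neither.

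Dilution by off time and early clustering also pull in opposite directions for the same events, as the 15.5% break-even in step 3 shows. They concern different event types and should not be added together.

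**Conclusion.** The concern holds as a weakness of the estimator and its definition. It does not establish that the rates are biased in one known direction. A primary objective whose sole aim is an accurate estimate has a summary that fits early surgical harm poorly, with no stated origin and no stated choice between cumulative and interval reporting. Its bound belongs to a different denominator.

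In the illustration, a cumulative rate falls 4.2-fold between the 1-month and 10-month visits while 11.1% of subjects remain affected. That size assumes an implant clock, complete follow-up and all events by the 1-month visit; later events would make the fall smaller. The dilution of about 16% at 10 months is conditional in the same way. The change should be made, although no pass or fail decision depends on it.

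**What to change.** Amend Objective 3 in section 5.2 as follows.

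1. **Main result.** Report the cumulative percentage of implanted subjects with at least one event by each visit, counted from the day of surgery. Do this separately for SADEs, device failures, and replacement, revision or explant.
2. **Bound.** Give each percentage the one-sided 95% exact binomial upper bound already planned, with subjects as the denominator. Where follow-up is incomplete, use a Kaplan-Meier estimate with its own one-sided bound.
3. **Secondary results.** Keep total event counts, including repeat events, because section 4.5.2 foresees more than one revision. If a person-month rate is kept, split it before and after activation, say whether it is cumulative or per interval, and use a Poisson bound.
4. **Retrospective charts.** State how the start, length and completeness of follow-up are determined for the commercial patients who bring the total to 109.

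The cost is a change of wording and slightly more analysis. The late-visit figures will look less favourable: 11.1% in the illustration, where the plan would show 0.94 per 100 person-months. Sections 4.6.1.2 and 4.8.2 place revisions and failures on the case report forms, but the forms are not in the documents. Whether all needed dates are collected, especially from the commercial charts, has to be confirmed.

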2.2 Investigational Sites and Number of Enrollments

The post-approval study will enroll a minimum of 45 new subjects on a consecutive consenting basis at 5 to 10 investigational sites to be implanted by newly-trained surgeons. These subjects will be evaluated for both efficacy and safety endpoints. The goal will be to monitor the subjects through their one (1) year follow-up. NOTE: In order to achieve the required sample size of 109 subjects for the safety endpoints, data from these 45 new subjects will be supplemented by data from a retrospective chart review of "commercial" (non-study subjects).

Trial Objectives

The overall objective of the study is to evaluate the safety and effectiveness of the *Esteem® System* implanted by newly-trained surgeons in subjects suffering from moderate to severe hearing loss.

Primary Objectives:

- 1) To demonstrate that the *Esteem® System* improves the speech threshold of sensitivity for hearing and identifying speech signals as well as or better than the pre-implant hearing aid (aided condition).
Endpoint: Comparison of the speech reception threshold (SRT) using the *Esteem® System* as compared to the pre-implant aided condition.
- 2) To demonstrate that the *Esteem® System* is as effective as or better than the hearing aid for improving speech discrimination (intelligibility) as shown by the word recognition score at 50 dB.
Endpoint: Comparison of word recognition score using the *Esteem®* as compared to the pre-implant aided condition.
- 3) To determine the incidence of Serious Adverse Device Effects (SADE) and Adverse Device Effects (ADE) and the incidence rate of device failures and replacements.
Endpoint: The analysis of the incidence of SADEs and device failures and replacements at each follow-up.
- 4) To demonstrate that the incidence of facial pareses/paralysis is no greater than the 7% incidence experienced in the PMA clinical trial.
Endpoint: The analysis of the incidence of facial pareses/paralysis at 1 month follow-up.
- 5) To demonstrate that the subjects' cochlear function remains unchanged with the *Esteem® System* as shown by comparison of the subjects' pre-implant baseline bone conduction threshold versus the subjects' post-activation visit bone conduction threshold.
Endpoint: Comparison of the bone conduction threshold with forehead placement compared to the pre-implant bone conduction threshold.

Secondary Objectives:

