If the subject requires a new hearing aid or the subject's own hearing aid settings were adjusted, the subject will need to return a minimum of 30 days later to ensure that the subject is well adjusted to the new hearing aid. When the subject returns, all screening and baseline testing will need to be tested / re-tested. If the subject's hearing aid is appropriately fit but does NOT pass the REM enrollment criteria, and the subject declines to return 30 days later to repeat all screening and baseline testing as required for the REM criteria, the subject may still be enrolled but their audiometric data will not be included in the analysis of study efficacy endpoints (safety and adverse event data at least through 1-month follow-up will still be included).

If the subject's hearing aid did not require adjustment, the subject can proceed with the remainder of the screening and baseline procedures.

Following the screening and baseline testing, if the subject meets all of the Inclusion/Exclusion Criteria, the subject will proceed with the *Esteem® System* Implant.

This study is a non-randomized clinical trial. If the pure tone average (average of 500, 1K and 2K) for both ears is within 5 dB, it will be up to the Investigator and the subject to select the ear that is to be implanted.

Esteem® Post Approval Study Pre-Screen Process

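### Objective 3 places an exact binomial bound on an events-per-person-month rate and names neither the binomial numerator nor its denominator

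*Combined protocol and SAP*

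**What the plan says.** Section 5.2, Objective 3, defines the estimate as the "observed number of SADEs and device failures and replacements over the total person-months of follow-up at each follow-up". The next sentence gives the interval: "The upper bound of the one-sided 95% exact binomial confidence interval on the SADE rate and device failure and replacement rate will be calculated". The objective is for estimation only: "There is no formal hypothesis".

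No section says what the binomial n is, whether the numerator is events or affected subjects, or how several events in one subject are handled. Objective 4, in the same section, uses the same kind of bound on a per-subject incidence at 1 month, where it fits.

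Other sections bear on follow-up and repeat events:

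- Section 2.2: to reach 109 safety subjects, "data from these 45 new subjects will be supplemented by data from a retrospective chart review". How long those chart-review subjects were followed is not given.
- Section 5.1: "For the facial pareses/paralysis objective with an end point of 1 month, a sample size of 109 subjects is required as shown below". The figure of 109 was therefore set for Objective 4.
- Section 4.2: for subjects who miss the hearing-aid fitting criterion and decline retesting, "safety and adverse event data at least through 1-month follow-up will still be included".
- Section 4.5.2 explains second procedures with the words "Due to the nature of Middle Ear surgery and potential requirements for multiple revisions".
- Section 4.8.1: "Device failures can result from hardware/software problems or surgical procedure problems".

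**The concern.** The estimate and its bound are different kinds of quantity. The estimate is a count divided by time at risk, so one subject can contribute several events and longer follow-up enlarges the denominator. An exact binomial bound describes n independent trials, each with at most one event. Two analysts could both follow the text and report different things: a bound per person-month, or a bound on the cumulative proportion of subjects.

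Objective 3 is a primary objective with no hypothesis, so the estimate and its bound are its whole result. They should share a scale, a denominator and a counting rule. Under the per-subject reading, a further risk is that a bound built on all 109 subjects takes no account of how long each was followed.

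**Working it through.** The plan gives no expected rate, event count or precision target for Objective 3, so there is no figure to reproduce. Event counts and follow-up lengths below are assumed for illustration.

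**Inputs.** Safety subjects 109 and new subjects 45 (sections 2.2 and 4.7), so chart-review subjects = 109 − 45 = 64. Follow-up to 1 year (section 2.2), so full follow-up = 109 × 12 = 1308 person-months.

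**Formulas, one-sided 95% upper bounds.**
- Exact binomial (Clopper-Pearson): BetaInv(0.95; x + 1, n − x).
- Exact Poisson: χ²(0.95; 2(x + 1)) / (2T), where T is person-months.

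**Reading 1: n = person-months.** With x = 5 and n = T = 1308, the estimate is 5/1308 = 0.00382 per month.
- Binomial: 0.00802 per month.
- Poisson: 21.026 / (2 × 1308) = 0.00804 per month.
- The gap is about 0.2%.

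This bound does depend on the time unit. For 10 events in 540 person-months (45 × 12), converted to a yearly rate, it is 0.3477 with years as trials, 0.3745 with months and 0.3769 with days. The Poisson bound is 0.3769 whatever the unit.

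**Reading 2: n = subjects.**
- 5 of 109 affected: 9.4%, a cumulative proportion that cannot be set beside 0.00382 per month.
- 8 events in 5 of 109 subjects: 12.9% if events are the numerator, 9.4% if affected subjects are.

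**Repeat events.** Coverage of the nominal 95% bound was simulated for 45 subjects over 12 months at a true 0.5 events per subject-year (100,000 runs). The binomial bound used events over subjects.
- Independent events: binomial 90.3%, Poisson 96.1%.
- Strong clustering within subjects (gamma shape 0.5): binomial 81.2%, Poisson 89.2%.

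**Unequal follow-up under reading 2, with n held at 109.** For 5 affected subjects the binomial bound stays at 9.4%. For comparison, the Poisson bound is converted to a 12-month risk as 1 − exp(−12 × bound), which assumes a constant rate:

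| Months for each of the 64 | Person-months | Poisson bound per month | 12-month risk |
|---|---|---|---|
| 12 | 1308 | 0.00804 | 9.2% |
| 9 | 540 + 576 = 1116 | 0.00942 | 10.7% |
| 6 | 540 + 384 = 924 | 0.01138 | 12.8% |
| 3 | 540 + 192 = 732 | 0.01436 | 15.8% |

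Now keep the 3-month row and let a share f of the 12-month hazard fall in the first 3 months. The bound on cumulative hazard is H = (21.026 / 2) / (45 + 64f), and the risk is 1 − exp(−H):

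| f | 45 + 64f | H | 12-month risk |
|---|---|---|---|
| 25% (constant rate) | 61.0 | 0.172 | 15.8% |
| 50% | 77.0 | 0.137 | 12.8% |
| 75% | 93.0 | 0.113 | 10.7% |
| 90% | 102.6 | 0.102 | 9.7% |

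The gap from 9.4% is therefore driven by two things the documents do not give: how long the chart-review subjects were followed, and when events occur.

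**The case against.** The best defence is that the sentence order favours person-months as n. On that reading the choice between binomial and Poisson changes the bound by a fraction of a percent. This stands, and it limits the point on that reading to a mislabelled method. It does not remove the ambiguity, because Objective 4 uses the same bound per subject.

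A reader might infer that the bound cannot be computed once events repeat. That is true only when events exceed n. Below that it can be computed, as the 12.9% shows, but its model does not hold.

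A reader might also infer that the plan understates 12-month risk by a wide margin, 9.4% against 15.8%. The documents do not support this. It needs n fixed at 109, only 3 months for every chart-review subject, and a constant rate. The plan analyses at each follow-up, so n could be the subjects followed to that visit. Chart-review follow-up is not stated, which is not the same as short. Section 1.4 has the 45 new subjects followed to 1 year for safety. The section 4.2 clause covers a narrow group and sets a floor, and the 1-month sizing in section 5.1 belongs to Objective 4.

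The evidence on repeat events is also partial. Section 4.5.2 classes revision surgery as a failure of the clinical procedure, which is not the same label as SADE, device failure or replacement. Section 4.8.1 makes overlap possible but does not establish it.

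Finally, exact Poisson is no cure for clustering. For 8 events in 1308 person-months it gives 0.0110 per month, against cluster-robust bounds of 0.0130 (subject counts 2, 2, 2, 1, 1) to 0.0152 (4, 1, 1, 1, 1). Those bounds are large-sample approximations resting on five affected subjects, so they serve as an optional check only.

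**Conclusion.** The mismatch is real as written: a person-time estimate carries a binomial bound, and neither numerator nor n is named. The consequence is minor. It is negligible if n is person-months. If n is subjects, the bound changes scale, moves with the counting rule, and does not account for unequal follow-up unless n is limited to those followed to the visit. Whether 12-month risk would be understated, and by how much, cannot be determined from the documents. No pass or fail decision depends on the bound. The mismatch itself rests on the text alone; every numerical illustration rests on assumed event counts and follow-up.

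**What to change.** In section 5.2, Objective 3:

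1. Keep events per person-month, state that every event counts, and replace the exact binomial bound with a one-sided 95% exact Poisson upper bound.
2. Report separately the proportion of subjects with at least one event by each visit, with a one-sided 95% exact binomial upper bound whose n is the subjects followed to that visit.
3. Show the number of subjects and person-months beside each figure.

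Optional: a bound that is cluster-robust by subject if anyone has more than one event, and a Kaplan-Meier estimate where follow-up is incomplete.

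The cost is a few sentences and one extra table. The 45 new subjects need no new data collection, and follow-up dates for the chart-review subjects are already needed for the planned person-month denominator.
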